### 7.3 LOST TO FOLLOW-UP

A participant will be considered lost to follow-up if he or she fails to respond to CBD Sleep Study Team.

The following actions must be taken if a participant fails to respond to CBD Sleep Study Team:

- CBD Sleep Study Team will attempt to contact the participant and ascertain if the participant wishes to and/or should continue in the study.
- Before a participant is deemed lost to follow-up, the investigator or designee will make every effort to regain contact with the participant (where possible, up to 3 telephone calls).
- Should the participant continue to be unreachable, he or she will be considered to have withdrawn from the study with a primary reason of lost to follow-up.

## 8 STUDY ASSESSMENTS AND PROCEDURES

### 8.1 EFFICACY ASSESSMENTS

We will enroll 150 study participants who display chronic insomnia defined as a self-reported difficulty initiating (latency to persistent sleep >30 min) and/or maintaining sleep (>30 min awake, or waking >30 min before desired waking time) on three or more nights per week for at least 3 months. Participants will also complete a brief clinically validated insomnia severity index, and only participants with an Insomnia Severity Index score >15 will be enrolled in Le Rêve 3.0. We will enroll males or females aged 25–70 years that are located in the United States that meet inclusion and exclusion criteria.

Le Rêve 3.0 will be conducted in an entirely decentralized manner. Primary data for Le Rêve 3.0 will be obtained in a completely unbiased manner from a non-invasive sleep-tracking wrist-worn device called “Whoop” (<https://www.whoop.com>), that electronically collects and transmits sleep data from study participants in the comfort of their own beds.

The wristband collects hundreds of data points per second from a 3-axis accelerometer, 3-axis gyroscope, and heart rate sensor. The wristband can accurately measure the latency to fall asleep, total sleep time, sleep fragmentation, as well as the time spent in each sleep stage [Light, Slow Wave (Deep), Rapid Eye Movement (REM), and Awake]. The device also collects data using photoplethysmography (PPG), a technique that involves measuring blood flow by assessing superficial changes in blood volume. Heart rate, heart rate variability and respiratory rate, can all be derived from PPG data, and all of these metrics are used in Whoop’s sleep detection and staging algorithms. Importantly, two recent publications, published independently from Whoop, show that data on sleep stages collected from the Whoop device are highly accurate and correlate well with polysomnography (PSG), the gold-standard of sleep tracking used in clinical studies conducted in sleep clinics.

The primary endpoint efficacy endpoint in Le Rêve 3.0 is the percentage of time spent in slow wave (Deep) and REM sleep as collected by a non-invasive wrist-worn sleep-tracking device called Whoop. Additional objective secondary outcome measures that will be collected on the Whoop device include: Total sleep time, sleep latency, the number of sleep disturbances, time spent in each sleep stage, and the percentage of time spent in each sleep stage.

A modified version of a clinically validated questionnaire entitled the PGI will be used to track subjective measures of sleep physiology. This data will be collected from study participants in the form of a brief five-minute survey that will be completed on their smartphone at the end of each four-week treatment period. This survey measures the perception of the study participants of the effects of treatment.

### 8.2 SAFETY AND OTHER ASSESSMENTS

**8.2.1** This is an interventional study to determine the effects of Defined CBD on sleep physiology.

**8.2.2** Defined CBD is a small capsule composed of vegetable cellulose (gluten-free, non-GMO, vegan, certified kosher, certified halal) that contains 300 mg of >99.9% purity hemp-derived CBD purified in a GMP-facility that is dissolved in coconut oil (USDA certified organic, non-GMO, dairy-free, gluten-free, vegan coconut oil) with a custom chemical formulation that contains a low concentration (1 mg each) of highly purified (>98% purity) terpenes linalool, myrcene, phytol, limonene,  $\alpha$ -terpinene,  $\alpha$ -terpineol,  $\alpha$ -pinene, and  $\beta$ -caryophyllene [Food Grade (GRAS), Natural, Organic, non-GMO, dairy-free, gluten-free, vegan]. Defined CBD contains no  $\Delta$ -9-THC.

**8.2.3** Defined Research Inc. has >5 years of experience in manufacturing CBD products under GMP-like conditions, and confirms the molecular composition of every batch of Defined CBD (including the Defined CBD to be used in Le Rêve 3.0) by an ISO-10725-accredited analytical testing laboratory. These analytical tests confirm the concentration and purity of Defined CBD, and ensure that it is free from any contaminants, including pesticides, residual solvents and heavy metals. Electronic records of these laboratory tests are stored at Defined Research and are available upon request.

**8.2.4** Based on a large amount of published clinical data, the World Health Organization (WHO) has established that CBD (the active ingredient in Defined CBD) is non-intoxicating and has an excellent safety profile in humans. Previous clinical studies indicate that adverse reactions with CBD are rare. The most common adverse reactions that occurred with CBD when given at a high dose [e.g., at the recommended dose for the FDA approved CBD drug Epidiolex® (20 mg/kg/day), were somnolence (sleepiness); decreased appetite; diarrhea; transaminase elevations; fatigue; malaise; asthenia (abnormal physical weakness or lack of energy); rash; insomnia; sleep disorder; poor quality sleep; and infections. However, these adverse reactions were only observed in >10% of patients at a CBD dose (20 mg/kg/day or ~1,800 mg for a 90 kg male) that is approximately six times greater than the dose that will be used in Le Rêve 3.0 study (300 mg or ~3 mg/kg/day for a 90 kg male). Moreover, the frequency of these adverse events decreased significantly when Epidiolex® was administered at a lower dose (10 mg/kg/day or ~900 mg for a 90 kg male), that is still three times the dose we will use in Le Rêve 3.0. A recent meta-analysis of adverse events from 12 clinical trials with CBD indicated that associations with abnormal liver function tests, somnolence, sedation and pneumonia were limited to childhood epilepsy studies, where CBD may have interacted with other medications such as clobazam and/or sodium valproate. After excluding studies in childhood epilepsy, the only adverse outcome associated with CBD treatment was diarrhea. And, again, this was only observed at doses well above the CBD dose that will be evaluated in Le Rêve 3.0. Therefore, if adverse events are observed with Defined CBD in Le Rêve 3.0, we presume that they will be minor and only occur at a lower frequency than what was observed in previous clinical studies.

Although rare, some adults display hypersensitivity to CBD. Participants with known hypersensitivity to CBD will be excluded from participating in Le Rêve 3.0. As noted above, some recent studies indicate that extremely high doses of CBD (much higher than what will be used in Le Rêve 3.0) might impair liver function. Therefore, as a precaution, study participants in Le Rêve 3.0 will be required to refrain from the use of any of the following contra-indicated drugs for at least one week prior to and for the duration of the study: erythromycin, clarithromycin, itraconazole, ketoconazole, posaconazole, voriconazole, ritonavir, telaprevir, boceprevir, amlodipine, gemfibrozil, cyclosporine, danazol, amiodarone, verapamil, diltiazem, rifampin, theophylline, tizanidine, bupropion, efavirenz, diflunisal, propofol, fenofibrate, lamotrigine, morphine, lorazepam, diazepam, clobazam, stiripentol, valproate, everolimus, sirolimus, or tacrolimus, and niacin (vitamin B3 greater than 1g/ day). Participants who cannot refrain from the intake of these contra-indicated drugs prior to and throughout the study will be excluded from participating in Le Rêve 3.0.

Defined CBD also contains low concentrations (1 mg each) of highly purified (>98%) forms of the terpenes linalool, myrcene, phytol, limonene,  $\alpha$ -terpinene,  $\alpha$ -terpineol,  $\alpha$ -pinene, and  $\beta$ -caryophyllene. Terpenes are widely used as fragrances and flavors in consumer products such as perfumes, cosmetics and cleaning products, as well as food and drink products. For example, the aroma and flavor of hops comes, in part, from sesquiterpenes (mainly  $\alpha$ -humulene and  $\beta$ -caryophyllene), which are used to make beer. Importantly, the terpenes in Defined CBD are designated by the FDA as GRAS (Generally Regarded as Safe) for oral human consumption. Although rare, some adults display mild skin allergies to terpenes when applied topically. Participants with known hypersensitivity to terpenes will be excluded from participating in Le Rêve 3.0.

## 8.3 ADVERSE EVENTS AND SERIOUS ADVERSE EVENTS

### 8.3.1 DEFINITION OF ADVERSE EVENTS (AE)

An adverse event (AE) is any untoward medical occurrence in a clinical study participant administered an investigational product, which does not necessarily have a causal relationship with the treatment. An AE can therefore be any unfavorable and/or unintended sign, symptom, or disease temporally associated with the use of an investigational product, whether or not considered related to the investigational product. AEs may also include pre- or post-treatment complications that occur as a result of protocol specified procedures or special situations (Section 8.3.8).

An AE does not include the following:

- Medical or surgical procedures such as surgery, endoscopy, tooth extraction, and transfusion. The condition that led to the procedure may be an adverse event and must be reported.
- Preexisting diseases, conditions, or laboratory abnormalities present or detected before the screening visit that do not worsen.
- Situations where an untoward medical consequence has not occurred (e.g. hospitalization for elective surgery, social and/or convenience admissions).
- Overdose without clinical sequelae (Section 8.3.8).
- Any medical condition or clinically significant laboratory abnormality with an onset date before the consent form is signed and not related to a protocol-associated procedure is not an AE. It is considered to be preexisting and should be documented as medical history.

### 8.3.2 DEFINITION OF SERIOUS ADVERSE EVENTS (SAE)

A SAE is defined as an event that, at any dose, results in the following:

- Death.
- Life-threatening (Note: The term “life-threatening” in the definition of “serious” refers to an event in which the participant was at risk of death at the time of the event; it does not refer to an event that hypothetically might have caused death if it were worse or more severe).

- New patient hospitalization due to the investigational product.
- Persistent or significant disability/incapacity.
- A medically important event or reaction: such events may not be immediately life-threatening or result in death or hospitalization but may jeopardize the participant or may require intervention to prevent one of the other outcomes constituting SAEs. Medical and scientific judgement must be exercised to determine whether such an event is a reportable under expedited reporting rules. Examples of medically important events include intensive treatment in an emergency room or at home for allergic bronchospasm; blood dyscrasias or convulsions that do not result in hospitalization; and development of drug dependency or drug abuse.

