### 8.3.3 CLASSIFICATION OF AN ADVERSE EVENT

The medical monitor is responsible for assessing AEs and SAEs for causality and severity, and for final review and confirmation of accuracy of event information and assessments.

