### 8.3.6 SERIOUS ADVERSE EVENT REPORTING

All SAEs, regardless of cause or relationship, that occur after the participant first consents to participate in the study (i.e. the signing of the informed consent) and throughout the duration of the study will be reported on the eCRFs.

The medical monitor will immediately report to Defined Research any SAE, whether or not considered study intervention related, and will include an assessment of whether there is a reasonable possibility that the study intervention caused the event. Study endpoints that are SAEs (e.g., all-cause mortality) must be reported in accordance with the protocol. All SAEs will be followed until satisfactory resolution or until the study investigator deems the event to be chronic or the participant is stable.

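### Hospitalization is serious only if caused by the product, so some unrelated admissions lose SAE status and the immediate report that 8.3.6 intends

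*Combined protocol and SAP*

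**What the plan says.** The protocol's section 8.3.2 defines an SAE by five outcomes: death, a life-threatening event, hospitalization, disability or incapacity, and a medically important event. The hospitalization item is worded "New patient hospitalization due to the investigational product". The medically important item describes its own scope with the words "such events may not be immediately life-threatening or result in death or hospitalization but may jeopardize the participant", and so mentions hospitalization alongside death with no causal condition.

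Section 8.3.6 sets the reporting duty. It covers "All SAEs, regardless of cause or relationship, that occur after the participant first consents to participate in the study", and adds: "The medical monitor will immediately report to Defined Research any SAE, whether or not considered study intervention related".

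Causality is handled elsewhere. Section 8.3.3 makes the medical monitor "responsible for assessing AEs and SAEs for causality and severity", and 8.3.3.2 gives the related / not related categories. Section 8.3.1 defines an AE as an event "whether or not considered related to the investigational product", and takes out of the AE definition situations without an untoward consequence, such as "hospitalization for elective surgery, social and/or convenience admissions".

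**The concern.** Seriousness and causality are normally two separate judgements: the first is about what happened to the participant, the second about why. Sections 8.3.1, 8.3.3 and 8.3.6 are written on that basis. The hospitalization item in 8.3.2 is not, because it makes the causal opinion part of the test for seriousness.

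At stake is how an affected admission is classified and how fast it is reported. The sponsor would not receive the immediate report, and the event would enter the safety dataset of section 9.3 as an AE. Other provisions also refer to SAE status: discontinuation of the intervention (7.1), withdrawal by the PI (7.2) and, as an example, breaking the blind for an individual (6.3). For this one criterion, the count of SAEs depends on a causality opinion formed before the event can be called serious.

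**Working it through.** No figure in the plan bears on this and no calculation applies beyond a count. The check sets the sections side by side.

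1. **Count of criteria (8.3.2).** Death: no causal condition. Life-threatening: none. Hospitalization: must be due to the product. Disability or incapacity: none. Medically important: none. So 1 of 5 carries a causal condition.

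2. **Trace an admission judged unrelated.** Suppose it is not fatal, life-threatening, disabling or medically important. It fails those four items on outcome and the hospitalization item on causality. It is not an SAE.

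3. **Apply 8.3.6.** Both the scope statement and the immediate-report duty start from an event that is already an SAE. This admission never reaches them. For the hospitalization criterion, the instruction to disregard relationship has no effect, because relationship has already been used to decide seriousness.

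4. **Look for a provision that restores SAE status.** Sections 8.3.1 to 8.3.6 contain none. Section 8.3.4 sends events that do not meet the SAE criteria to the eCRF as AEs, with no immediate-report duty.

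5. **Which admissions can be judged unrelated?** Two kinds are clear.
   - On treatment: section 8.3.3.2 allows a not related call where another cause has been established.
   - Between consent and first dose: 8.3.6 opens SAE reporting at consent, and the schedule in section 1.3 places screening and baseline data collection before treatment. An admission in that period cannot be due to a product not yet taken, so the hospitalization item can never apply to it.

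6. **Is the phrase needed as a filter?** Its obvious use would be to keep out planned or social admissions. Section 8.3.1 already removes these from the AE definition, so deleting the phrase does not bring them in.

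7. **What is kept?** Section 8.3.4 requires AEs on study to be documented whatever their relationship, and 8.3.5 requires AE reporting once treatment has begun. An affected on-treatment admission is therefore still recorded.

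**The case against.** The strongest reply is that few admissions would slip through. Section 8.3.3.2 treats a temporal relationship as sufficient for a related call, so many on-treatment admissions could qualify on timing alone. The medically important item reaches events that may jeopardize the participant, which could cover many acute admissions. Both points stand and narrow the class. They do not close it: 8.3.3.2 still allows a not related call when another cause is established, the protocol never equates being due to the product with being related (plainly read, the former is stricter), and the medically important item rests on judgement and does not include hospitalization as such.

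A second reply is that 8.3.2 and 8.3.6 do not formally contradict each other, since 8.3.6 governs whatever 8.3.2 admits. That is correct as logic. But 8.3.6 plainly intends relationship not to matter, and for one criterion 8.3.2 defeats that intention.

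A third is that no data are lost. Daily text messages are meant to capture AEs and SAEs (10.1.7), and 9.4.4 puts all collected data into the safety summaries. This also stands for on-treatment events: the loss is of classification and speed of reporting.

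Two stronger readings are tempting.

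- A reader might infer that the start dates in 8.3.4, 8.3.5 and 8.3.6 cannot be reconciled. The documents do not support this. Section 8.3.4 speaks of reportable events; if the first day of the study means consent, only SAEs are reportable before treatment and both AEs and SAEs afterwards. What remains is an undefined term, and some tension with the statement in 8.3.4 that all AEs on study are documented.
- A reader might infer from the AE definition, "any untoward medical occurrence in a clinical study participant administered an investigational product", that no pre-dose event can be an SAE. That goes too far: 8.3.1 allows for some pre-treatment complications and uses consent as the boundary for pre-existing conditions, and 8.3.2 defines an SAE simply as an event.

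**Conclusion.** The point holds in a limited form and should be fixed. As written, one of the five SAE criteria carries a causal condition. An admission judged unrelated that meets no other criterion is not an SAE and does not trigger the immediate report.

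The conclusion rests on reading the hospitalization item literally and on the absence of any provision that restores serious status. How many admissions are affected cannot be estimated, because the documents give no admission rate; the class is narrowed as described above.

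It would be wrong to infer that every unrelated admission loses serious status, since those that are fatal, life-threatening, disabling or medically important remain SAEs. It would also be wrong to infer that on-treatment admissions go unrecorded, or that a planned comparison is distorted: the plan specifies no between-treatment test of SAEs.

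**What to change.** In 8.3.2, delete the five words that tie hospitalization to the investigational product, so that the item rests on outcome like the other four. Assess relationship separately under 8.3.3.2. No change to the 8.3.1 exclusions is needed.

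As a minor clarification, define the first day of the study in 8.3.4 so that it agrees with the AE start in 8.3.5 (initiation of treatment) and the SAE start in 8.3.6 (consent).

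The cost is a wording amendment, which the Statement of Compliance says the IRB must approve before it is implemented, and possibly more events classified and immediately reported as SAEs. No visit, endpoint or sample size changes.

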### 8.3.3 CLASSIFICATION OF AN ADVERSE EVENT

The medical monitor is responsible for assessing AEs and SAEs for causality and severity, and for final review and confirmation of accuracy of event information and assessments.

#### 8.3.3.1 SEVERITY OF EVENT

The following guidelines will be used to describe severity using the CTCAE (Common Terminology Criteria for Adverse Events) grading system:

- **Grade 1 Mild** – Events require minimal or no treatment and do not interfere with the participant's daily activities.
- **Grade 2 Moderate** – Events result in a low level of inconvenience or concern with the therapeutic measures. Moderate events may cause some interference with functioning.
- **Grade 3 Severe** – Events interrupt a participant's usual daily activity and may require systemic drug therapy or other treatment. Severe events are usually potentially life-threatening or incapacitating. Of note, the term "severe" does not necessarily equate to "serious".
- **Grade 4 Life Threatening** – Events in which urgent medical intervention is indicated.
- **Grade 5 Death** – If related to the event.

#### 8.3.3.2 RELATIONSHIP TO STUDY INTERVENTION

The medical monitor is responsible for assessing the relationship to study drug using clinical judgement and the following considerations:

- **Not related:** There is not a reasonable possibility that the administration of the study intervention caused the event, there is no temporal relationship between the study intervention and event onset, or an alternate etiology has been established.
- **Related:** The AE is known to occur with the study intervention, there is a reasonable possibility that the study intervention caused the AE, or there is a temporal relationship between the study intervention and event. Reasonable possibility means that there is evidence to suggest a causal relationship between the study intervention and the AE.

### 8.3.3.3 EXPECTEDNESS

The medical monitor is responsible will be responsible for determining whether an AE is expected or unexpected. An AE will be considered unexpected if the nature, severity, or frequency of the event is not consistent with the risk information previously described for the study intervention (see Section 8.2.4).

### 8.3.4 TIME PERIOD AND FREQUENCY FOR EVENT ASSESSMENT AND FOLLOW-UP

The occurrence of an AE or SAE may come to the attention of study personnel during interviews of a study participant presenting for medical care, or upon review by a study monitor.

All AEs including local and systemic reactions not meeting the criteria for SAEs will be captured on the appropriate electronic case report form (eCRF). Information to be collected includes event description, time of onset, medical monitor's assessment of severity, relationship to study product, and time of resolution/stabilization of the event. All AEs occurring while on study must be documented appropriately regardless of relationship. All AEs will be followed to adequate resolution.

Any medical condition that is present at the time that the participant is screened will be considered as baseline and not reported as an AE. However, if the study participant's baseline medical condition worsens at any time during the study, it will be recorded as an AE.

Changes in the severity of an AE will be documented to allow an assessment of the duration of the event at each level of severity to be performed. AEs characterized as intermittent require documentation of onset and duration of each episode.

The medical monitor will record all reportable events (AEs and SAEs) starting with the first day of the study until the study is completed. The medical monitor will follow up with the study participant up to three times until resolution or stabilization.

